7.5.1 Subject Withdrawal

During the conduct of the study, the Sponsor will review the safety data for trends and signals that would indicate the need for withdrawal of a subject. The Investigator may withdraw a subject from the study for any of the following reasons:

- For any of the specific criteria listed in Section 7.5.3;
- Pregnancy;
- For any reason judged by the Investigator to be inappropriate to continue in the study, including a subject who is unable to communicate or cooperate with the Investigator, who has/had a psychiatric illness, disability or social situation that may compromise the safety of the subject during the study or affect the ability of the subject to adhere to study procedures;
- The study is terminated by the Sponsor;
- Any therapy-related event that is deemed life-threatening, regardless of intensity;
- Protocol noncompliance;
- Withdrawal of consent.

Should a subject decide to withdraw after administration of the investigational product (KHK4083 or placebo), or should the Investigator(s) decide to withdraw the subject, all efforts will be made to complete and report the observations up to the time of withdrawal as thoroughly as possible. A complete final evaluation at the time of the subject's withdrawal should be completed and an explanation given as to why the subject is withdrawing or being withdrawn from the study.

The reason for withdrawal must be collected. If the reason for withdrawal is a clinical AE, whether considered to be related to investigational product or not, the AE must be monitored until the return to the subject's baseline condition or until clinically satisfactory resolution is achieved (e.g., Grade 1 or stable). The clinical course of the AE will be followed according to accepted standards of care or medical practice, even after the end of the period of observation until a satisfactory explanation is found or the Investigator considers it medically justifiable to terminate follow up (e.g., event returned to subject's baseline, Grade 1, or stable).

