7.5.3 Criteria for Subject Removal from Treatment and the Study

In the absence of a medical contraindication or significant protocol violation, every effort will be made by the Investigator to keep the subject in the study. However, if the Investigator concludes that it is in the best interest of the subject to discontinue administration of the investigational product, including subjects who have not benefited from treatment or should

the subject decide to discontinue study treatment, all efforts will be made to complete and report the observations as thoroughly as possible.

Investigational product administration will be stopped if any of the following events occur:

- Subject experiences a second SUSAR of the same SOC;
- Subject experiences a severe AE that is related to the investigational product;
Investigational product administration may be withheld for up to 2 weeks if the subject experiences a severe event in which it is unclear if the event is related to the investigational product. This will allow the Investigator to determine if the event is related to the investigational product prior to removing the subject permanently from the study.
- Subject experiences a severe, acute infusion reaction despite administration of a prophylactic pre-medication regimen or if the subject experiences anaphylaxis regardless of having received a pre-medication regimen or not. Anaphylaxis has symptomatic bronchospasm and/or allergy-related edema/angioedema as the principal clinical manifestation(s); refer to the clinical diagnostic criteria of anaphylaxis defined in Appendix 5);
- Subject has two consecutive visits during Induction Therapy with a worsening from Baseline in partial Mayo Clinic score of ≥ 3 points (e.g., partial Mayo Clinic score of 3 at baseline, 6 at Week 2, and 6 at Week 4) or two consecutive visits during maintenance therapy with a worsening from Week 12 in partial Mayo Clinic score of ≥ 3 points at a visit and ≥ 5 points at the next visit unless the Investigator, with agreement from the Sponsor, determines that there has not been clinically significant worsening, in which case the subject may continue to receive study medication at that visit (agreement from the Sponsor is to be obtained for each visit);
- Surgery and/or use of prohibited medications are needed to treat the worsening of UC;
- Subject requires a concomitant medication that is prohibited in the study;

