- Subject has any clinical AEs, laboratory abnormality, intercurrent illness, or other medical condition that indicates to the Investigator that continued participation is not in the best interest of the subject. The Investigator should make a distinction between AEs that may require only interruption of treatment and those that require discontinuation;
- Subject decides to withdraw consent from the study in the absence of a medical need to withdraw as determined by the Investigator;
- Subject is noncompliant in the opinion of the Investigator;
- Administrative reasons; or
- If pregnancy is suspected while the subject is receiving investigational product, the treatment must immediately be withheld until the result of pregnancy testing is known. If pregnancy is confirmed, the investigational product will be permanently discontinued and the subject withdrawn from the study.

In the case of pregnancy, the Investigator must immediately notify the Sponsor of this event and record the pregnancy on the Pregnancy Surveillance Form. The Sponsor must also be

notified if a partner of a study subject becomes pregnant while the subject was receiving the investigational product. Reasonable attempts will be made to follow the pregnancy to conclusion in order to obtain information regarding the outcome.

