7.5.4 End-of-Treatment Visit

An End-of-Treatment visit must be conducted for all subjects who discontinue from treatment. This visit must occur within 2 weeks or 4 weeks after the last dose of investigational product of Induction Therapy or OLE/LTE Therapy, respectively.

If the subject discontinues during Induction Therapy, the assessments listed in Table 9.1 for End-of-Treatment/Week 12 should be performed at the End-of-Treatment visit. A sigmoidoscopy will be performed at End-of-Treatment/Week 12 if the subject discontinues more than 8 weeks after Baseline visit; the sigmoidoscopy may be performed up to 4 weeks after the last dose of study medication. Post-treatment follow-up visits should subsequently occur 4, 8 and 14 weeks after the End-of-Treatment/Week 12 visit.

If the subject discontinues during OLE/LTE therapy, the assessments listed in Table 9.2 for End-of-Treatment/Week 52 should be performed at the End-of-Treatment visit. A sigmoidoscopy will be performed at End-of-Treatment/Week 52 if the subject discontinues more than 8 weeks after the Week 12 visit; the sigmoidoscopy may be performed up to 8 weeks after the last dose of study medication. Post-treatment follow-up visits should subsequently occur 4, 8 and 12 weeks after the End-of-Treatment/Week 52 visit.

The Investigator must complete all applicable End-of-Treatment visit procedures (e.g., sigmoidoscopy, safety laboratory parameters, ECG, physical examination, vital signs) and applicable eCRF pages for subjects who discontinue treatment and include the reason for discontinuation of treatment.

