7.5.5 End-of-Study Visit

If the subject is withdrawn from the study, and thus no subsequent visits are planned, then the Investigator must complete all applicable final visit procedures (e.g., safety laboratory procedures, ECG, physical examination, vital signs) and applicable eCRF pages for subjects who discontinue treatment and include the reason for discontinuation of treatment. If the subject discontinues during the Induction Therapy, the assessment listed in Table 9.1 for Follow-up 3 should be performed at the End-of-Study visit. If the subject discontinues during OLE/LTE Therapy, the assessments listed in Table 9-2 for Follow-up 3 should be performed at the End-of -Study visit.

If the End-of-Study visit is the same as the End-of-Treatment visit then the End-of-Treatment visit assessments should be performed and the End-of-Treatment visit will also be the End-of-Study (end-of-trial) visit.

Once subjects discontinue participation from the study, they will revert to the care of their usual physician for treatment/management of their condition/disease as appropriate.

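### Sections 7.5 and 7.5.1 let the investigator turn a drug-stopping event into study withdrawal; Section 7.5.5 then plans no further visits, so part of the 16-week safety follow-up is lost for that subject

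*Protocol*

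**What the plan says.** **Stopping drug.** Protocol Section 7.5.3 lists events that end investigational product. They include a severe related AE, anaphylaxis, worsening on the partial Mayo score and need for a prohibited medication. With exceptions for medical contraindication or significant protocol violation, it asks that "every effort will be made by the Investigator to keep the subject in the study".

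**Follow-up after stopping drug.** Section 7.5.4 requires an End-of-Treatment visit within 2 weeks (induction) or 4 weeks (OLE/LTE) of the last dose. For induction: "Post-treatment follow-up visits should subsequently occur 4, 8 and 14 weeks after the End-of-Treatment/Week 12 visit". For the extension: "Post-treatment follow-up visits should subsequently occur 4, 8 and 12 weeks after the End-of-Treatment/Week 52 visit".

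**Leaving the study.** Section 7.5.1 says the investigator may withdraw a subject from the study. One listed reason is "For any of the specific criteria listed in Section 7.5.3"; another is "Any therapy-related event that is deemed life-threatening, regardless of intensity"; a third is any reason the investigator judges to make continuing inappropriate. The opening of Section 7.5 gives a general right to withdraw subjects for illness, AEs, well-being or noncompliance. The severe-AE bullet of Section 7.5.3 allows a pause to settle causality "prior to removing the subject permanently from the study". Confirmed pregnancy is an explicit exit: "If pregnancy is confirmed, the investigational product will be permanently discontinued and the subject withdrawn from the study".

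**What follows an exit.** Section 7.5.5 begins "If the subject is withdrawn from the study, and thus no subsequent visits are planned" and provides one final visit, which may coincide with the End-of-Treatment visit.

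**The commitment.** Sections 6.3, 10.6 and 12.5 each state that all subjects are assessed for AEs until 16 weeks after the last dose.

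**The concern.** Stopping study drug and leaving the study are different events, and Sections 7.5 and 7.5.1 let the investigator treat the first as grounds for the second. The subjects concerned are those stopped for toxicity, worsening disease or noncompliance. The first of these groups matters most in Part A, whose primary objective is safety and tolerability. Section 6.3 justifies the safety plan partly because its follow-up can detect late-appearing adverse effects.

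Under Section 10.6.5.1 AEs are elicited by asking at visits, so without visits there is no routine inquiry. SAP Section 8.1 counts any AE with onset on or after first dosing as treatment-emergent. Table 14.3.1-1.2 covers double-blind treatment plus follow-up, and SAP Section 9.2 takes N from the analysis set. A withdrawn subject therefore stays in N while new non-serious AEs and later antibody findings can be missed, as with any dropout.

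**Working it through.** **1. The 16 weeks reproduce.** For completers, the last dose and last follow-up visit are Weeks 10 and 26 (induction only) or Weeks 48 and 64 (OLE/LTE): 26 − 10 = 16 and 64 − 48 = 16 weeks. For treatment discontinuers under Section 7.5.4, with End-of-Treatment at its latest permitted time, visit time after last dose = End-of-Treatment time + interval:

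| Phase | Follow-up 1 | Follow-up 2 | Follow-up 3 |
|---|---|---|---|
| Induction | 2 + 4 = 6 | 2 + 8 = 10 | 2 + 14 = 16 |
| OLE/LTE | 4 + 4 = 8 | 4 + 8 = 12 | 4 + 12 = 16 |

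The default route therefore delivers the commitment. If End-of-Treatment falls earlier, the last visit comes correspondingly earlier.

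**2. Loss if the subject is released at End-of-Treatment.**
- Induction: (16 − 2)/16 = 14/16 = 87.5% of the window has no planned visit.
- OLE/LTE: (16 − 4)/16 = 12/16 = 75%.
- Visits from End-of-Treatment onward: 3 of 4 are lost.

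Release at a later follow-up visit loses less.

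**3. What remains and what goes.**

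| Remains after withdrawal | Source |
|---|---|
| Reporting of serious AEs to 16 weeks after last dose | 10.6.7 |
| Follow-up of AEs already known | 10.6.7 |
| Follow-up of the AE that caused removal | 7.5.1, 8.1.5, 9.4 |
| Repeat testing of clinically important abnormal laboratory results | 10.6.1 |
| One exit visit with laboratory tests, PK, antibody and partial Mayo | 7.5.5, Tables 9-1, 9-2, 10.4.1-1, 10.4.1-2 |

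Lost: active inquiry about new non-serious AEs, and the laboratory, PK, antibody and partial Mayo assessments at the later visits.

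**4. Scale.** One subject is 1/9 = 11.1% of a Part A dose arm, or 1/27 = 3.7% of those planned at the recommended dose. These are shares of an arm, not effects. Simulated steady-state trough over peak in Table 8.1.3-1 is 10.9/36.9 = 30%, 62.1/140.0 = 44% and 385.0/645.0 = 60% at 1.0, 3.0 and 10 mg/kg. Substantial drug is thus still present two weeks after a dose. These ratios hold only for 2-weekly dosing at steady state, not for 4-weekly extension dosing or a subject stopped early in induction.

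**The case against.** The strongest reply is that the plan already does what is wanted. Section 7.5.4 makes the End-of-Treatment visit mandatory and schedules follow-up; Section 7.5.3 presses for retention; SAP Section 5.1 counts treatment and study discontinuation separately. Section 10.6.5.2 restates the severe-AE rule as discontinuing product, so the Section 7.5.3 phrase about removal from the study is probably loose wording. Section 8.4 also separates stopping treatment after unblinding from a later decision on withdrawal. Some Section 7.5.3 items, such as withdrawn consent and confirmed pregnancy, are study exits in themselves, so the cross-reference in Section 7.5.1 has some legitimate use. All of this stands, and it keeps the point small.

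It does not close the gap. The retention clause carries exceptions that could cover a subject with anaphylaxis or a severe related AE, and the permission in Section 7.5.1 has no condition attached. By contrast, Section 7.5.2 keeps 16 weeks of safety follow-up for dosed subjects even if the whole study is terminated.

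A reader might infer that the protocol requires study exit whenever drug is stopped, or that safety follow-up then ceases altogether. Neither is supported: the withdrawal wording in Section 7.5.1 is permissive, and the duties in step 3 of the working survive.

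The Appendix 6 chart on follow-up after discontinuation is not visible in the text available. Its footnotes cover only End-of-Treatment timing and endoscopy, but the chart may say more.

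**Conclusion.** The concern holds as a conditional gap. If an investigator uses study withdrawal instead of stopping drug alone, the all-subject AE assessment in Sections 6.3, 10.6 and 12.5 is not fully delivered for that subject. At worst this removes 14 of 16 weeks (induction) or 12 of 16 weeks (OLE/LTE) of visit-based follow-up. Those figures assume End-of-Treatment at its latest permitted time and release at that visit.

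The documents give no basis for estimating how often this would occur or whether it would differ between arms, so a claim of biased safety comparisons would go too far. The Week 12 primary endpoint, the Week 4 and Week 6 escalation reviews and the induction-only AE tables (14.3.1-1.3, 14.3.1-2.2) are little affected. This is a low-cost improvement, not a flaw that threatens the trial's conclusions. Confidence is medium, chiefly because Appendix 6 cannot be read.

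**What to change.** Deleting the cross-reference in Section 7.5.1 would not be enough, because the general right in Section 7.5 and the broad-judgement reason in Section 7.5.1 lead to the same exit. The changes needed are:

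- **Sections 7.5, 7.5.1 and 7.5.3:** state that an investigator decision based on a Section 7.5.3 event, an AE, a life-threatening therapy-related event or noncompliance ends investigational product only. The subject then keeps the Section 7.5.4 visits to 16 weeks after the last dose. The exceptions are withdrawn consent, a subject who cannot be followed, or a documented investigator judgement that the visits themselves would do harm.
- **Section 7.5.1:** remove the reference to the Section 7.5.3 criteria.
- **Section 7.5.3:** in the severe-AE bullet, speak of permanently stopping product, in line with Section 10.6.5.2.
- **Section 7.5.5:** confine the path without further visits to those exceptions.
- **Confirmed pregnancy:** stop product and keep safety follow-up to 16 weeks.
- **Appendix 6:** make the chart show the same path.

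The cost is a protocol amendment, with ethics approval under Section 13.1 across the seven named countries, and some extra visits for subjects whom sites would otherwise release. The visits are already scheduled in Section 7.5.4. Section 8.5.1 already allows otherwise prohibited UC treatments during follow-up, so a subject who needs one can remain.

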7.5.2 Study or Investigative Site Termination

The Sponsor reserves the right to terminate the study at any time. Investigators have the responsibility to comply with International Conference on Harmonisation (ICH) E6-Good Clinical Practice (GCP) guidance. The Safety Monitoring Committee (refer to Section 6.3) may recommend termination of the study if the overall risk to subject safety is deemed to be unacceptable, including but not limited to serious or severe infection rates $\geq 40\%$ in the first cohort of 12 treated subjects (5/12) and similarly in subsequent cohorts. In addition, 2 subjects with two or more Suspected Unexpected Serious Adverse Reactions (SUSARs) of the same System Organ Class (SOC) may result in a recommendation to terminate the study.

In the event the study will be terminated, the Sponsor must promptly inform the hospital or clinic director of all participating institutions, Investigators, and regulatory authorities in writing. The Investigator is responsible for notifying subjects, stopping subject screening and dosing immediately, and providing appropriate medical care. Subjects dosed will be followed for safety for 16 weeks post-treatment and AE resolution. The Sponsor or the IRB/IEC may terminate the study for the following (but not limited to) reasons:

- Important safety findings, such as SAEs, which may influence subjects' well-being; or
- Other newly obtained information or reason(s) that may affect continuation of study.

The Sponsor or the IRB/IEC may terminate an investigative site for the following (but not limited to) reasons:

- Failure of the Investigator to comply with pertinent ICH E6-GCP guidelines and regulations;
- If serious protocol violations occur;
- Submission of knowingly false information from the research facility to the Sponsor, Medical Monitor, or other party involved in the study;
- Failure of the Investigator to enroll subjects into the study at an acceptable rate as agreed to with the Sponsor; or
- Repeated failure to have eCRF data completed and ready for submission to the Sponsor in the agreed-upon time.

7.5.3 Criteria for Subject Removal from Treatment and the Study

In the absence of a medical contraindication or significant protocol violation, every effort will be made by the Investigator to keep the subject in the study. However, if the Investigator concludes that it is in the best interest of the subject to discontinue administration of the investigational product, including subjects who have not benefited from treatment or should

the subject decide to discontinue study treatment, all efforts will be made to complete and report the observations as thoroughly as possible.

Investigational product administration will be stopped if any of the following events occur:

- Subject experiences a second SUSAR of the same SOC;
- Subject experiences a severe AE that is related to the investigational product;
Investigational product administration may be withheld for up to 2 weeks if the subject experiences a severe event in which it is unclear if the event is related to the investigational product. This will allow the Investigator to determine if the event is related to the investigational product prior to removing the subject permanently from the study.
- Subject experiences a severe, acute infusion reaction despite administration of a prophylactic pre-medication regimen or if the subject experiences anaphylaxis regardless of having received a pre-medication regimen or not. Anaphylaxis has symptomatic bronchospasm and/or allergy-related edema/angioedema as the principal clinical manifestation(s); refer to the clinical diagnostic criteria of anaphylaxis defined in Appendix 5);
- Subject has two consecutive visits during Induction Therapy with a worsening from Baseline in partial Mayo Clinic score of ≥ 3 points (e.g., partial Mayo Clinic score of 3 at baseline, 6 at Week 2, and 6 at Week 4) or two consecutive visits during maintenance therapy with a worsening from Week 12 in partial Mayo Clinic score of ≥ 3 points at a visit and ≥ 5 points at the next visit unless the Investigator, with agreement from the Sponsor, determines that there has not been clinically significant worsening, in which case the subject may continue to receive study medication at that visit (agreement from the Sponsor is to be obtained for each visit);
- Surgery and/or use of prohibited medications are needed to treat the worsening of UC;
- Subject requires a concomitant medication that is prohibited in the study;
- Subject has any clinical AEs, laboratory abnormality, intercurrent illness, or other medical condition that indicates to the Investigator that continued participation is not in the best interest of the subject. The Investigator should make a distinction between AEs that may require only interruption of treatment and those that require discontinuation;
- Subject decides to withdraw consent from the study in the absence of a medical need to withdraw as determined by the Investigator;
- Subject is noncompliant in the opinion of the Investigator;
- Administrative reasons; or
- If pregnancy is suspected while the subject is receiving investigational product, the treatment must immediately be withheld until the result of pregnancy testing is known. If pregnancy is confirmed, the investigational product will be permanently discontinued and the subject withdrawn from the study.

In the case of pregnancy, the Investigator must immediately notify the Sponsor of this event and record the pregnancy on the Pregnancy Surveillance Form. The Sponsor must also be

notified if a partner of a study subject becomes pregnant while the subject was receiving the investigational product. Reasonable attempts will be made to follow the pregnancy to conclusion in order to obtain information regarding the outcome.

7.5.4 End-of-Treatment Visit

An End-of-Treatment visit must be conducted for all subjects who discontinue from treatment. This visit must occur within 2 weeks or 4 weeks after the last dose of investigational product of Induction Therapy or OLE/LTE Therapy, respectively.

If the subject discontinues during Induction Therapy, the assessments listed in Table 9.1 for End-of-Treatment/Week 12 should be performed at the End-of-Treatment visit. A sigmoidoscopy will be performed at End-of-Treatment/Week 12 if the subject discontinues more than 8 weeks after Baseline visit; the sigmoidoscopy may be performed up to 4 weeks after the last dose of study medication. Post-treatment follow-up visits should subsequently occur 4, 8 and 14 weeks after the End-of-Treatment/Week 12 visit.

If the subject discontinues during OLE/LTE therapy, the assessments listed in Table 9.2 for End-of-Treatment/Week 52 should be performed at the End-of-Treatment visit. A sigmoidoscopy will be performed at End-of-Treatment/Week 52 if the subject discontinues more than 8 weeks after the Week 12 visit; the sigmoidoscopy may be performed up to 8 weeks after the last dose of study medication. Post-treatment follow-up visits should subsequently occur 4, 8 and 12 weeks after the End-of-Treatment/Week 52 visit.

The Investigator must complete all applicable End-of-Treatment visit procedures (e.g., sigmoidoscopy, safety laboratory parameters, ECG, physical examination, vital signs) and applicable eCRF pages for subjects who discontinue treatment and include the reason for discontinuation of treatment.

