- The design of the safety plan permits a comparison of the safety response to KHK4083 under baseline and post-KHK4083 administration conditions in the same subject.
- The design of the safety plan allows a comparison of this study's safety data set with the Phase 1a/1b study (4083-001).
- The safety monitoring follow-ups permit the evaluation of late appearing adverse effects that may emerge or progress after the administration of KHK4083.
- The measures used to assess safety are well-defined and reliable, and the proposed safety analyses are adequate to assess the effects of the administration of KHK4083.

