8.1.5 Post-treatment Follow-up Period

Post-treatment Follow-up assessments will continue for 16 weeks after the last infusion associated with the subject's treatment period. For subjects who only receive Induction Therapy (i.e., last dose at Week 10 and do not continue in OLE/LTE Therapy), the Post-treatment Follow-up visits will be at Weeks 16, 20, and 26. For all subjects who receive both Induction Therapy and OLE/LTE Therapy (last dose at Week 48), the Post-treatment Follow-up visits will be at Weeks 56, 60, and 64. Subjects removed from the study for AEs will be followed until there is a return to the subject's baseline condition, or until a clinically satisfactory resolution is achieved. The date of the subject's last post-treatment study visit will be considered the End-of-Study date.

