9.4 Post-treatment Follow-up Period

A safety Post-treatment Follow-up Period will continue for 16 weeks after the last infusion associated with the subject's treatment period and will include 3 Post-treatment Follow-up visits. For subjects who only receive Induction Therapy (i.e., do not continue in OLE/LTE Therapy), the Post-treatment Follow-up visits will be at Weeks 16, 20, and 26. For all subjects who receive both Induction Therapy and OLE/LTE Therapy, the post-treatment follow-up visits will be at Weeks 56, 60, and 64. A partial Mayo Clinic score (without sigmoidoscopy) including the Physician's Global Assessment, which is to be performed after

review of all available clinical data, and the results from the IBDQ will be recorded at each visit during the Treatment Period. Subjects removed from the study for AEs will be followed until there is a return to the subject's baseline condition, or until a clinically satisfactory resolution is achieved. Safety measurements will be performed from KHK4083 (or placebo) administration until the final safety follow-up assessment. In addition, the following will be collected during the Post-treatment Follow-up Period according to the schedule of study events in Table 9-1 (Induction Therapy) and Table 9-2 (OLE/LTE Maintenance Therapy):

- Brief physical examination (Section 10.6.4);
- Vital signs (systolic and diastolic blood pressure, radial pulse, and respiration rate) and body temperature (oral) (Section 10.6.2);
- Body weight (Section 10.6.4);
- Adverse events (Section 10.6.5);
- Concomitant medications (Section 8.5);
- Clinical laboratory evaluations (refer to Section 10.6.1 for list of tests): Blood samples will be collected at specified times for serum chemistry, hematology, and the multiplex-31 assays (i.e., if the subject does not continue in OLE Therapy); urine samples will be collected for urinalysis;
- PK sampling at the time of the follow-up visits (refer to Table 10.4.1-1 and Table 10.4.1-2 for schedule of days/times for sample collection);
- PD assessment - wr-CRP testing at follow-up visit (Week 26 or Week 64);
- Immunogenicity assessment - serum samples at the time of the follow-up visits (Section 10.4.2).

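### Follow-up of subjects who stop treatment early is counted from an End-of-Treatment visit with no earliest date, so the last visit can fall at 14 weeks (Induction) or 12 weeks (OLE/LTE) after the last dose instead of 16

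*Protocol*

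**What the plan says.** Protocol section 8.1.5 sets the duration: "Post-treatment Follow-up assessments will continue for 16 weeks after the last infusion". Section 9.4 repeats it: "A safety Post-treatment Follow-up Period will continue for 16 weeks after the last infusion". Footnote b to Table 9-2 says the same for the OLE. AE assessment (6.3, 10.6, 12.5) and SAE reporting (10.6.7) also run to 16 weeks after the last dose.

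For subjects who discontinue treatment, section 7.5.4 first times the End-of-Treatment visit: "This visit must occur within 2 weeks or 4 weeks after the last dose of investigational product of Induction Therapy or OLE/LTE Therapy, respectively". It then counts follow-up from that visit. For Induction: "Post-treatment follow-up visits should subsequently occur 4, 8 and 14 weeks after the End-of-Treatment/Week 12 visit". For OLE/LTE: "Post-treatment follow-up visits should subsequently occur 4, 8 and 12 weeks after the End-of-Treatment/Week 52 visit".

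The legible footnotes of Appendix 6 repeat the 2- and 4-week upper limits and give no earliest date. Under section 8.1.5 the last post-treatment visit is also the End-of-Study date.

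**The concern.** The offsets in 7.5.4 are those of the completers. They give 16 weeks for completers because End-of-Treatment is then nominally fixed at 2 weeks (Induction) or 4 weeks (OLE/LTE) after the last infusion. For a discontinuer that visit may come at any time up to the limit, and each week it comes early takes a week off follow-up. A site could follow 7.5.4 exactly and close a subject out before 16 weeks.

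Section 6.3 rests part of its justification of the safety plan on follow-up: "The safety monitoring follow-ups permit the evaluation of late appearing adverse effects that may emerge or progress after the administration of KHK4083". Investigators ask about AEs at visits (10.6.5.1), and the follow-up visits carry hematology, chemistry, urinalysis and, per 9.4, "Immunogenicity assessment - serum samples at the time of the follow-up visits". After an early last visit, a new event would come to light only if the subject reported it unprompted, and a new laboratory change or anti-drug antibody would not be sampled.

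An early End-of-Treatment visit is plausible. Among the stopping rules in 7.5.3 are anaphylaxis and severe infusion reaction despite pre-medication. These arise during or soon after an infusion, so the visit could follow within days.

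**Working it through.** **Inputs.** Last dose at Week 10 (Induction) or Week 48 (OLE/LTE), and completers' follow-up at Weeks 16, 20, 26 or 56, 60, 64 (8.1.5). End-of-Treatment limits and follow-up offsets (7.5.4). Visit windows (Tables 9-1 and 9-2). Simulated half-lives (Table 8.1.3-1).

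**The plan's own figure.** Completers: 26 − 10 = 16 weeks and 64 − 48 = 16 weeks, so the stated 16 weeks is reproduced. Measured from Week 12 and Week 52, completers' visits fall at 4, 8, 14 and 4, 8, 12 weeks, identical to the offsets in 7.5.4.

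**Discontinuers.** Let *e* be the weeks from last dose to End-of-Treatment. The last visit is at *e* + 14 (Induction, *e* from 0 to 2) or *e* + 12 (OLE/LTE, *e* from 0 to 4).

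| *e* (weeks) | Induction: last visit | Shortfall | OLE/LTE: last visit | Shortfall |
|---|---|---|---|---|
| 0 | 14 | 2 | 12 | 4 |
| 1 | 15 | 1 | 13 | 3 |
| 2 | 16 | 0 | 14 | 2 |
| 3 | – | – | 15 | 1 |
| 4 | – | – | 16 | 0 |

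**Comparison with completers at the edge of their windows.**
- Induction: Week 10 dose 4 days late and Week 26 visit 7 days early gives (112 − 4 − 7)/7 = 14.4 weeks.
- OLE/LTE: Week 48 dose 7 days late and Week 64 visit 7 days early gives (112 − 7 − 7)/7 = 14.0 weeks.

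The Induction worst case (14.0) is therefore close to what a completer may already have. The OLE/LTE worst case (12.0) is 2 weeks below it. Section 7.5.4 gives no window for discontinuers' visits. If ±7 days is assumed, the minimums become (98 − 7)/7 = 13.0 and (84 − 7)/7 = 11.0 weeks.

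**Residual drug, Induction only, illustrative.** Share of the level at the last dose = 2^(−days / half-life), at 98 and 112 days:

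| Dose | Half-life (days) | 14 weeks | 16 weeks |
|---|---|---|---|
| 10 mg/kg | 26.2 | 7.5% | 5.2% |
| 3.0 mg/kg | 16.3 | 1.6% | 0.9% |
| 1.0 mg/kg | 10.5 | 0.2% | 0.1% |

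This assumes first-order decline at half-lives simulated for dosing every 2 weeks, and section 8.1.3.1 reports that elimination depends on dose. No half-life is tabulated for dosing every 4 weeks, so no OLE/LTE figure is offered.

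**The case against.** The best reply is that the 16-week rule is stated repeatedly and the offsets add up to it (2 + 14, 4 + 12). A site holding End-of-Treatment late in its window satisfies every section, and one finishing at 12 weeks would breach 8.1.5 and 9.4. On this reading the wording is loose but the plan is not for shorter follow-up. That is right about intent. But 7.5.4 is the only legible text that dates discontinuers' visits. The general sections give a duration without a visit that delivers it.

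Appendix 6 is titled for exactly this population, and its diagram, which could not be seen, may date the visits correctly. That stands as a reservation. If so, 7.5.4 should still be brought into line with it.

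The effect is also small. The extremes need End-of-Treatment on the day of the last infusion, and a stop decided at the next dosing visit leaves little or no gap. The reporting duty to 16 weeks holds regardless. Existing AEs are followed to an outcome, and section 8.1.5 adds: "Subjects removed from the study for AEs will be followed until there is a return". Important laboratory abnormalities are repeated until resolved, acceptable or explained (10.6.1). The Week 12 primary endpoint is untouched. All of this stands. It limits the loss to new findings in the final weeks, but it does not reconcile the two rules.

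**Conclusion.** The concern holds. As written, 7.5.4 allows the last scheduled visit 14 to 16 weeks (Induction) or 12 to 16 weeks (OLE/LTE) after the last dose, against a stated 16. The nominal shortfall is 0 to 2 or 0 to 4 weeks, and the material part is in OLE/LTE. It concerns scheduled visits and their assessments only. It does not concern the reporting duty, nor subjects withdrawn from the study with no further visits (7.5.5).

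The conclusion rests on the End-of-Treatment visit having no earliest date, which is what the text and the legible Appendix 6 footnotes show. The number of subjects affected is unknown. This is a modest gap in safety observation that should be closed because the protocol's own rule already calls for it.

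**What to change.** In 7.5.4, and in Appendix 6 if its diagram differs, set Follow-up 3 at 16 weeks after the last dose, with the usual visit window, whatever the date of End-of-Treatment. Follow-up 1 and 2 can stay at 4 and 8 weeks after End-of-Treatment.

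The text change is two sentences, carried in a protocol amendment with its usual ethics review, and there are no added visits. For the few subjects affected, the last visit moves up to 2 weeks (Induction) or 4 weeks (OLE/LTE) later. The interval from Follow-up 2 to Follow-up 3 becomes 16 − (*e* + 8) = 8 − *e* weeks: 6 to 8 in Induction (now 6) and 4 to 8 in OLE/LTE (now 4).

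If an 8-week interval is thought too long, Follow-up 2 can be placed midway between Follow-up 1 (*e* + 4) and Follow-up 3 (16), at 10 + *e*/2 weeks after the last dose. Both intervals are then 6 − *e*/2, at most 6 weeks. That equals the longest interval now used in Induction but is longer than the present 4 weeks in OLE/LTE. This refinement is optional.
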